6.1.1 Consent Process

The study may be explained by the fetal cardiology team prior to the last prenatal encounter. Maternal consent will be obtained by a person (research coordinator or another physician) who has no direct involvement in the care of this patient at the second last (generally 28-30 weeks) visit or at the time of the last fetal exam (≥ 34 weeks). Moreover, it will be explained that she can drop out of the study at any time. Once enrolled, participants (mother and child) will be assigned individual study numbers to allow de-identified data entry in a password protected Excel database that will be securely stored on the SickKids server and be accessible to the research team only.

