In the event of an AE, we will use a variety of sources of information to identify possible side effects of the MH including direct observations, imaging data, participant reports, laboratory reports and other medical reports. The PI and study team will evaluate the circumstances and clinical correlation of the events. If a serious and unexpected AE occurs that is deemed to be possibly related to the use of MH (e.g. fetal death within a day of the oxygen administration), we will discontinue the use of supplementary oxygen to that study participant as applicable, immediately place the study on hold indefinitely, and the PI will report the case to the DSMB and Health Canada.

In the case of a moderate AE that is considered possibly related to the intervention (e.g. cardiac dysfunction such as fetal bradycardia of less than 90 beats per minute for more than 1 minute), we will discontinue the administration of oxygen in that study participant and the DSMB will review the event at their next scheduled meeting, and continue to enrol other patients for the study.

If an AE is mild, we will discontinue the oxygen supplementation to that study participant, but continue enrolling other patients for the study. Examples of mild maternal AEs that will result in discontinuation of oxygen administration for a subject will include fatigue, nasal or oral dryness or minor nasal bleeding and skin irritation.

In the event that oxygen supplementation is discontinued as a result of an AE, the study participant will not undergo oxygen supplementation at a later time and will be withdrawn from the study. Any data that is collected up until the point of withdrawal will be kept.

We do not expect ductal occlusion to occur within 45 minutes of fetal exposure to saturations that are lower when compared with a neonate. In the unlikely event ductal constriction occurs, it will be reversible once the MH is discontinued.

d) Expectedness assessment:

Unexpected	If the nature, severity or frequency of an event is not consistent with the risk information listed in the Material Safety Data Sheet
-------------------	---

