AEs and SAEs related to oxygen administration will be documented by the site investigator. Prior to the start of oxygen administration, a thorough medical history should be obtained to document all preexisting maternal symptoms, complaints and health concerns. As many pregnancy related symptoms are intermittent in nature, a thorough history including variations in severity and frequency should be taken. AEs and SAEs should be reassessed at each participant encounter. If signs or symptoms remain similar to baseline or are less in severity, frequency, or both, they will be considered within the usual range and do not need to be documented as AEs. In contrast, signs and symptoms that are new or, if preexisting, are more frequent/severe, need to be documented, assessed for severity and causality, and followed up until resolution.

In addition, the following table of endpoints will be used for the study:

Unexpected fetal demise	Stop the study; review by DSMB, PI and collaborators
Detection of cardiac dysfunction	Discontinue the exam – observe until resolved Review by PI and collaborators
Fatigue, dry/bloody nose, skin irritation	Review by PI and collaborators

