9.3.2 Study Withdrawal

A subject is free to withdraw from participation in the trial at any time, for any reason, specified or unspecified, and without prejudice. If the subject withdraws, data that has already been

collected up to that point in time will be kept (as indicated in the patient informed consent).

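### Stopping oxygen for an adverse event also withdraws the participant, and the plan does not provide for collecting the newborn's outcome afterwards

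*Combined protocol and SAP*

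**What the plan says.** Section 7 (Assessment of Adverse Events) sets the rule. When an AE leads to oxygen being stopped, "the study participant will not undergo oxygen supplementation at a later time and will be withdrawn from the study". The next sentence reads: "Any data that is collected up until the point of withdrawal will be kept".

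The rule reaches down to minor complaints: "If an AE is mild, we will discontinue the oxygen supplementation to that study participant". The examples given are tiredness, a dry nose or mouth, a small nosebleed and irritated skin. The moderate example is fetal: a heart rate below 90 beats per minute for more than one minute.

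Section 9.3.2 (Study Withdrawal) has a matching sentence for voluntary withdrawal. Data already "collected up to that point in time will be kept (as indicated in the patient informed consent").

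A table later in section 7 covers some of the same events. The row headed "Fatigue, dry/bloody nose, skin irritation" gives only review by the principal investigator and collaborators. The cardiac dysfunction row says "Discontinue the exam – observe until resolved", followed by the same review. Section 7 also says that new or worse signs "need to be documented, assessed for severity and causality, and followed up until resolution".

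Section 6.1.1 states that "participants (mother and child) will be assigned individual study numbers", for de-identified data entry. Section 6.2 names the health chart as a data source.

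**The concern.** MH is both the exposure and the diagnostic test. The outcomes it is meant to predict are survival to discharge (section 4.3), the morbidity score (section 6.1.4) and neonatal compromise (section 8). All of them occur weeks after the test. A rule that ends participation at the test therefore acts before any outcome exists.

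The pairs affected are not a random subset. Section 4.1 sets out to characterise the response to MH and relate it to neonatal outcome. A fetus that develops bradycardia under oxygen is showing a response of exactly that kind. If its outcome is not collected, an informative case leaves the descriptive summary. If some MH measurements had already been made, it also leaves the association and ROC analyses. Stops for mild maternal discomfort are different: they lose cases but give little reason to expect bias. Both losses are avoidable, because the newborn's course is recorded in the chart whether or not oxygen was stopped.

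**Working it through.** **Order of events.**
- Exposure: late gestation, on two occasions, echocardiography and MRI (section 2.3).
- Possible stop and withdrawal: during either occasion (section 7).
- Outcomes: birth to discharge (sections 4.3, 6.1.4 and 8), and to 1 year for some pulmonary hypertension cases (section 4.3).
- Collection after withdrawal: not provided for in any section. Follow-up of an AE to resolution concerns the event, not the neonatal outcome.

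**The plan's own figures.** Section 8 gives 22 of 70 (31%) compromised and 1–3% with pulmonary hypertension. For N = 50:
- compromised: 50 × 22/70 = 15.7 (plan: 15)
- not compromised: 50 × 48/70 = 34.3 (plan: about 35)
- pulmonary hypertension: 50 × 0.01 to 50 × 0.03 = 0.5 to 1.5 (plan: 1)

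These reproduce.

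**Expected number of stops.** The stop rate p is an assumption; the documents give none. Expected stops = 50p. Chance of at least one = 1 − (1 − p)^50. Expected compromised newborns among those stopped, if stopping is unrelated to outcome, = 50p × 22/70.

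| Assumed p | Expected stops | Chance of at least one | Compromised among stopped |
|---|---|---|---|
| 0% | 0 | 0% | 0 |
| 1% | 0.5 | 39% | 0.16 |
| 2% | 1.0 | 64% | 0.31 |
| 5% | 2.5 | 92% | 0.79 |

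**Precision.** For an assumed area under the ROC curve of 0.80, the Hanley–McNeil 95% half-width is 0.144 with 50 pairs. It is 0.146 with 49 (2% lost) and 0.148 with 47.5 (5% lost), so loss unrelated to outcome costs almost nothing.

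**Extreme selective loss.** Suppose all k stopped pairs are compromised and every one has a usable MH result. Take an illustrative sensitivity of 12/15 = 80%. Section 5.2 recruits until 50 have successfully completed but does not define completion, so there are two cases.

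*Stopped pairs do not count towards the 50.* Completers show 12/15. Over all who started, sensitivity lies between 12/(15 + k) and (12 + k)/(15 + k).

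*Stopped pairs count towards the 50.* The value over all who started is 12/15. Completers show between (12 − k)/(15 − k) and 12/(15 − k).

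| k | Not counted: value over all who started | Counted: value seen in completers |
|---|---|---|
| 1 | 75.0–81.3% | 78.6–85.7% |
| 2 | 70.6–82.4% | 76.9–92.3% |
| 3 | 66.7–83.3% | 75.0–100% |

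The exact 95% interval for 12/15 is 51.9–95.7%. Only the 100% corner at k = 3 falls outside it.

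**Why these are upper bounds.** Section 6.1.2 allows 5 minutes for steady state before MH measurement. Sections 6.1.2 and 6.1.3 take no research measurements once MH has ended. A pair stopped in the first 5 minutes of its first MH session has no MH result, so knowing its outcome cannot return it to the ROC analysis. Only pairs with usable MH data, such as a completed echocardiogram before a stop in the MRI, can move sensitivity. Three or more stops is also unlikely at modest rates. At p = 2% the chance is 1 − 0.364 − 0.372 − 0.186 = 0.078, about 8%, before requiring that all three be compromised.

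**The case against.** The strongest reply is that the loss is inferred. Sections 7 and 9.3.2 say what is kept; neither forbids later chart collection. Section 9.3.2 points to the consent form for the data terms, and that form was not available. These newborns go to the same critical care unit regardless. This stands as a limit on certainty. It does not remove the point: staff are told to withdraw the participant and are nowhere told to keep collecting. A reader might infer that the plan prohibits outcome collection; the text does not say so. Nor do the separate study numbers for mother and child settle whether the child is withdrawn too.

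A reader might also infer that the section 7 table contradicts the text. It is introduced as an addition to the text. The mild row does not say oxygen continues, and the cardiac row does not exclude withdrawal or review by the data and safety monitoring board (DSMB). The rows are better called incomplete.

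Third, it could be inferred that safety information is lost. It is not: AEs are followed to resolution, and fetal demise is a listed endpoint (Protocol Summary) that triggers review.

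Finally, section 8 plans descriptive statistics for a small feasibility study, and recruiting to 50 completers may restore the number. It would not restore the particular cases removed.

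**Conclusion.** The point holds as a minor design weakness. The withdrawal rule is explicit, all neonatal outcomes follow it, and no outcome collection after it is stated. The probable result is missing outcomes for pairs who did not tolerate MH, including any fetus with a cardiac event during the test.

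The effect is likely small and may be zero. Section 7 reports no AEs in the literature or the centre's own experience, and with no stops nothing is lost. It would be tempting to conclude that the diagnostic accuracy result will be materially biased. The documents do not support that: the stop rates, the number stopped and the 12/15 sensitivity are all assumed. The ranges also require every stopped pair to be compromised and to have a usable MH result. Bias is plausible mainly where a fetal event caused the stop after some MH data had been obtained. The case for acting rests on the low cost of the change and on there being only about 15 compromised newborns to learn from.

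**What to change.** In section 7, replace the withdrawal clause with wording such as: *will receive no further study oxygen, but mother and child will remain in chart follow-up to the planned outcome unless consent is withdrawn.* The rule that stops oxygen stays unchanged.

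In section 8, state that stopped pairs with a usable MH measurement are included, flagged, in the outcome analysis, and that safety and descriptive outcome are reported for all who started MH.

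As minor tidying, complete the table rows for cardiac dysfunction and mild maternal AEs so that they match the text: stop oxygen in both, with DSMB review for moderate events.

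I would not redefine completion in section 5.2 for this purpose. Accepting a single MH exam would let pairs with echocardiography alone fill the 50, and section 2.4 intends to combine both modalities.

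The cost is one sentence in section 7, a short addition to section 8, two table rows and a change to the consent wording if it does not already allow this. Outcomes come from charts already in use. The downside is a few pairs with incomplete MH imaging.

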8. STATISTICS

This is an observational cohort study to test whether acute MH is a useful diagnostic test for fetal TGA. This requires confirmation of the study concept that among TGA fetuses there will be specific hemodynamic and structural characteristics and responses that will be associated with neonatal compromise shortly after birth. Neonatal compromise is defined as any of these outcomes: pre-op/BAS mortality; minimal pre-BAS pH ≤ 7.1 , SaO₂ $\leq 40\%$, PaO₂ ≤ 25 mmHg, maximal serum lactate ≥ 10 mmol; and/or PPHN (combined pre-operative reverse differential cyanosis $\geq 30\%$ and/or postoperative RVp $\geq 75\%$ systemic ≥ 48 h post-surgery or $\geq 50\%$ at postoperative discharge). Twenty-two (31%) of 70 consecutive newborns born at Mount Sinai Hospital for fetal TGA/IVS fulfilled at least one of the outcomes ([name] et al. AEPC 2016). PPHT affects 1-3% of children with TGA. Based on these data we would expect about 35 cases without severe neonatal compromise, 15 cases with neonatal compromise and 1 case with PPHT.

Simple descriptive statistics will be adequate for this small feasibility and safety study. Data obtained from this study will further help to describe the possible ranges in hemodynamic findings at baseline and during MH in a larger cohort of TGA patients and in comparison with our previous data. The comparison between pre and post MH variables will be analysed using the Brand Altman's plot. Receiver operating statistics will be used to test the diagnostic value of MH.

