4.3 Study Endpoints

Study endpoints are any of the following outcomes: survival to discharge from Hospital as a primary outcome. A secondary outcome will be any evidence of perinatal compromise as defined in the protocol. This will be associated with the fetal response to oxygen. For cases with PPHT with RV pressure $>50\%$ of the systemic pressure at the time of discharge, the outcome to 1 year of life will be ascertained.

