6.1.4 Neonatal Data

Newborns with antenatally diagnosed TGA are routinely transferred to the Critical Care Unit immediately after their delivery for the preoperative management. Unless a VSD is large enough to allow discharge home with adequate oxygen saturations and to delay surgery to later in infancy, a neonatal ASO is the treatment of choice and mainly completed during the first week of life. Early neonatal preoperative procedures may include BAS and/or the use of IV prostaglandin to improve the oxygen saturation. Less commonly, intubation, ventilation or even ECMO may also be required prior to the surgical intervention. As measure of patient morbidity, a composite

score of 10 variables will be used, assigning a value of 1 for each event that occurred between birth to hospital discharge or in-hospital death respectively: 1) respiratory distress syndrome requiring surfactant; 2) cardiopulmonary resuscitation requiring chest compressions; 3) cerebral vascular injury (intra-ventricular or -parenchymal hemorrhage, ischemic stroke); 4) necrotizing enterocolitis; 5) need of ECMO; 6) infections associated with health care (bloodstream, surgical site, and urinary tract infection); 7) unplanned re-intubation; 8) re-operation for residual cardiac lesions; 9) interventional catheterization for residual cardiac lesions; and 10) unplanned intensive care readmission.

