6.3 Collected Patient Data

A) Prenatal Echocardiography

- Date of exam (dd/mmm/yyyy)
- Gestational age at exam (weeks/days)
- Estimated fetal weight (g)
- MPA valve diameter
- Aortic valve diameter

Imaging variables at baseline and with MH:

Atrial septal morphology (2D; 4D) and foramen flow (color; 4D flow)

FO diameter

Septal excursion

Shunt description

Branch PA flow (mid-portion)

peak flow

VTI

PI (peak systolic velocity – end-diastolic velocity/mean velocity)

PV Doppler flow:

VTI

MPA:

VTI

Heart rate

LCO

AAo:

VTI

Heart rate

RCO

DA flow (color and Doppler):

minimal diameter

reversed end-diastolic flow: yes – no

systolic peak flow

forward-reverse flow ratio

flow restriction: yes - no
MCA Doppler flow
peak flow
VTI
PI
UA Doppler flow
Peak flow
VTI
PI

RV and LV (4D): volumes

B) Fetal MRI

- Date of exam
- Gestational age at exam (weeks+days)
- Fetal weight estimation (g)
- Fetal weight Z-score
- Fetal weight percentile
- Brain volumetry (mL) (baseline; 3D steady state)
- Placenta volumetry (mL)
- Estimated HCT
- UV
- DAo
- Ventricle (specify R or L)
- Imaging variables at baseline and with MH

Cardiovascular oximetry (SatO₂):

LV

MPA

RV

AAo

DAo

UV

SVC

Fluximetry (ml/min/m²):

AAo

DA

Main PA

RPA

LPA

SVC

IVC

UV

DA

Brain (ml/min/m²):

cDO₂
cVO₂
Fetus (ml/min/m²)

DO₂
VO₂

Placenta Volumetry
T2 star

Patient Safety during MH

- Adverse events

C) Postnatal Outcomes

- Date of birth (dd/mmm/yyyy)
- Delivery place
- Gestational age at birth
- Weight at birth
- Placental weight at birth
- APGAR score (1 and 5 minutes)
- PaO₂ and SpO₂
- Age at CCU admission
- Neonatal interventions: stat BAS, oxygen, intubation/ventilation, ECMO, other
- Neonatal PGE: yes – no; time of start
- Neonatal BAS: yes – no; age at procedure
- Pre-op/pre-BAS: hemoglobin; minimal pH; minimal preductal PaO₂; peak lactate
- Pre-BAS compromise (defined as minimal pre-BAS pH \leq 7.1, SaO₂ \leq 40%, PaO₂ \leq 25 mmHg, maximal serum lactate \geq 10 mmol): yes - no
- Pre-BAS echo: ASD and VSD size, shunting, and gradients
- Persistent pulmonary arterial hypertension (defined as combined pre-operative reverse differential cyanosis \geq 30% and/or postoperative RVp \geq 75% systemic \geq 48h post-surgery and/or \geq 50% at postoperative discharge): yes – no
- Pre-op complications: organ failure; NEC, cerebro-vascular injury; death
 - o Date of event
 - o Age at event
- Date of surgery
- Age at surgery
- Type of surgical repair: ASO; VSD closure, other

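### A raised postoperative RV pressure is enough to establish PPHN, and so neonatal compromise, without residual outflow or branch PA obstruction being ruled out

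*Combined protocol and SAP*

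**What the plan says.** Section 8 makes the composite an any-of rule: "Neonatal compromise is defined as any of these outcomes". PPHN is one of its components. The PPHN definition starts with "combined pre-operative reverse differential cyanosis" of at least 30% and continues with "and/or postoperative RVp" of at least 75% of systemic 48 h or more after surgery, or at least 50% at postoperative discharge.

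Section 6.3 C uses the same limits for its yes/no field: "Persistent pulmonary arterial hypertension (defined as combined pre-operative reverse differential cyanosis", again joined to the RV pressure limits by and/or. The only gradients named in that list belong to the pre-BAS echocardiogram. No postoperative RV pressure value, outflow or branch PA gradient, or pulmonary artery pressure is listed.

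Residual surgical lesions are foreseen elsewhere. The morbidity score in Section 6.1.4 has items for re-operation and for "interventional catheterization for residual cardiac lesions", but nothing connects these to the PPHN definition. The outflow obstruction exclusion in Section 5.3 is a fetal eligibility criterion and cannot cover a surgical result.

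Section 4.3 asks for outcome to 1 year: "For cases with PPHT with RV pressure" above 50% "of the systemic pressure at the time of discharge". Section 8 plans receiver operating statistics for the diagnostic value of maternal hyperoxygenation (MH).

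**The concern.** After an arterial switch the RV ejects through the reconstructed pulmonary outflow. Its pressure rises with pulmonary vascular disease, but also with obstruction at the outflow or in the branch pulmonary arteries. That is general physiology, not a statement in the documents. Under the written rule, an infant with normal pulmonary artery pressure beyond a stenosis, and RV pressure at or above the limit, is coded PPHN = yes and compromise = yes.

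This label is used to judge scenario 4 in Section 2.4, which expects PPHN to go with an unchanged fetal pulmonary flow and pulsatility under maternal oxygen. There is no evident reason why a surgical stenosis should follow from that fetal response. Such an infant would therefore tend to count against scenario 4 for a reason unrelated to it. The infant would also enter the compromise group, although Section 8 describes that outcome as arising soon after birth.

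**Working it through.** **Inputs from the documents.** N = 50 (protocol summary). Historical compromise rate: "Twenty-two (31%) of 70 consecutive newborns" (Section 8). PPHT in 1-3% of children with TGA (Sections 2.1 and 8). Section 8 expects 35 without compromise, 15 with compromise and 1 with PPHT.

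**The plan's own figures.**
- Compromise: 50 × 22/70 = 15.7 (plan: 15).
- No compromise: 50 × 48/70 = 34.3 (plan: 35).
- PPHT: 50 × 0.01 = 0.5 to 50 × 0.03 = 1.5 (plan: 1).

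These agree to within rounding. The three counts add to 51, so the PPHT case is presumably one of the 15. The chance of at least one true PPHT case is 1 − 0.99^50 = 0.39 at 1% and 1 − 0.97^50 = 0.78 at 3%.

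**What one infant does to the PPHN label.** With T true cases and one case explained by obstruction, the false share is 1/(1 + T).
- T = 0.5: 1/1.5 = 67%
- T = 1: 1/2 = 50%
- T = 1.5: 1/2.5 = 40%

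**Range over an assumed rate.** Let q be the proportion of infants, among those not truly positive, whose residual obstruction brings RV pressure to a stated limit. The documents give no value, so q = 1-10% is an assumption.
- False PPHN labels = 50 × (1 − 0.02) × q, with true PPHN at 2% (1 case). True share = 1/(1 + false labels).
- Extra false compromise cases = 34.3 × q. Only infants not already positive by another route can be added.
- Apparent AUC = w × 0.80 + (1 − w) × 0.50, where w = 15.7/(15.7 + extra). The 0.80 is assumed. Falsely labelled infants are taken to respond to MH as non-cases do.

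| q | False PPHN labels | True share of PPHN labels | Extra false compromise cases | Apparent AUC |
|---|---|---|---|---|
| 1% | 0.5 | 67% | 0.3 | 0.794 |
| 2% | 1.0 | 51% | 0.7 | 0.787 |
| 5% | 2.5 | 29% | 1.7 | 0.770 |
| 10% | 4.9 | 17% | 3.4 | 0.746 |

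**Against sampling error.** The Hanley-McNeil standard error at AUC 0.80 with 15 cases and 35 non-cases uses 0.80/1.20 = 0.667 and 2 × 0.64/1.80 = 0.711. The variance is [0.16 + 14 × (0.667 − 0.64) + 34 × (0.711 − 0.64)]/(15 × 35) = 0.0056, so the standard error is about 0.075. At AUC 0.85 the same formula gives about 0.067. The largest loss in the table, 0.80 − 0.746 = 0.054, is below either.

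**The case against.** Several points on the other side stand.

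- **RV pressure is not the only route.** A reader might infer that PPHN rests on postoperative RV pressure alone. It does not: pre-operative reverse differential cyanosis is a separate route. RV pressure is sufficient without confirmation, not the sole criterion. The word combined in the definition is unclear, but and/or does not require both.
- **Not every residual lesion counts.** Only infants who reach 75% from 48 h, or 50% at discharge, are affected.
- **Section 4.3 does not define PPHN.** It adds an RV pressure condition for infants already classed as PPHT. A mislabelled infant would reach the 1-year follow-up only through the definition in Sections 6.3 C and 8.
- **The planning rate may already contain such cases.** The 22 of 70 were counted on the same list of outcomes, so treating all 15.7 as true cases and adding more may count some infants twice.
- **The analysis is modest.** Survival to discharge is the primary outcome, the study is described as a small feasibility and safety study, and Section 8 does not name the ROC reference outcome. With about one PPHN case expected, scenario 4 cannot be tested statistically under any definition.
- **Part of the information is recoverable.** Re-operation and catheter intervention are recorded, and Section 6.2 gives charts and echocardiography images as sources. Obstruction left untreated before discharge is not captured by those items.

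These points limit the size of the concern. They do not supply the missing condition. Investigators may exclude stenosis by judgement, but nothing written asks them to, so coding could vary between infants.

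**Conclusion.** The gap in the definition is real, and closing it is a cheap improvement. Sections 6.3 C and 8 allow RV pressure to establish PPHN and compromise with no check for obstruction, and no listed field would reveal the error afterwards.

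The harm falls mainly on the PPHN label. With 0.5 to 1.5 true cases expected, a single obstruction-explained infant makes 40-67% of the labels false. That much needs no assumed obstruction rate, only that one such infant occurs.

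For the composite the effect is small. At an assumed q of 1-10% it is 0.3 to 3.4 extra cases on 15.7 and an AUC loss of about 0.01 to 0.05, less than one standard error. It also assumes that the composite is the ROC reference outcome. A reader might infer that most PPHN labels will be surgical stenoses, or that the ROC result will be seriously distorted. The documents support neither: they contain no rate of residual obstruction, and the composite figures are modest even at the top of the assumed range.

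**What to change.** In Sections 6.3 C and 8, count the RV pressure routes as PPHN only when residual outflow or branch PA obstruction does not explain the pressure. Add two fields to 6.3 C, taken from existing postoperative echocardiograms: RV pressure, and the RV outflow or branch PA gradient. Report infants whose RV pressure is explained by obstruction separately, as residual lesions. Name the ROC reference outcome, and repeat the ROC analysis without the RV pressure routes as a sensitivity analysis. Section 4.3 needs only its above-50% limit reconciled with the at-least-50% limit in Sections 6.3 C and 8.

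The cost is wording in two sections, one limit reconciled in a third, two data fields and one extra analysis. Two downsides are minor. Gradients across serial or branch stenoses are approximate, so an occasional infant will be unclassifiable and should be reported as such. Comparability with the 31% planning rate is slightly reduced. The change affects how outcomes are classified, not patient care.

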4.1 Primary Objective

The primary objective is to examine and characterize the response, or lack thereof, to acute MH as a diagnostic test on intracardiac/ductal shunting and pulmonary blood flow among fetuses with TGA, and to clarify its associations with measures of neonatal outcomes.

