4.2. Secondary Objectives

A secondary objective will focus on the acute effects of MH on the cerebral perfusion.

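### The baseline-versus-MH comparison is assigned to a Bland-Altman plot, which does not give the precision of the within-fetus change; ROC, the only method named for the link to outcome, does not give its size by group

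*Combined protocol and SAP*

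**What the plan says.** Section 8 contains the whole analysis plan, in three statements:

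- General approach: "Simple descriptive statistics will be adequate for this small feasibility and safety study". A stated aim is to "describe the possible ranges in hemodynamic findings at baseline and during MH".
- Baseline against MH: "The comparison between pre and post MH variables will be analysed using the Brand Altman" plot (evidently Bland-Altman).
- Link to outcome: "Receiver operating statistics will be used to test the diagnostic value of MH". No index variable or interval is named.

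Section 6.1.2 adds that percent changes in VTIs and PIs will be derived from the echocardiograms, without saying how they will be summarised.

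These methods have to serve two objectives. The primary one (section 4.1) is to "examine and characterize the response, or lack thereof, to acute MH as a diagnostic test" and "to clarify its associations with measures of neonatal outcomes". The secondary one (section 4.2) reads: "A secondary objective will focus on the acute effects of MH on the cerebral perfusion". Sections 2.4 and 4.3 also say that prenatal findings, and the response to oxygen in particular, will be related to the neonatal course. They name no method.

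On numbers, section 8 says "we would expect about 35 cases without severe neonatal compromise, 15 cases with neonatal compromise".

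**The concern.** A Bland-Altman plot asks whether two measurements of the same quantity can be used interchangeably. That is not the question here. The protocol expects MH to change the measurements: section 2.3 cites a 30 to 50% rise in flow to the lungs in normal fetuses, and section 2.4 predicts a branch-PA PI fall of at least 10% when atrial shunting is unrestricted. The quantity of interest is how large the change is, how well it is known, and whether it differs between fetuses who later become compromised and those who do not.

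The plan could be followed to the letter and report a mean line, scatter limits and an ROC area. The reader would then have no interval for the mean change, no change by outcome group and no estimate of the difference. A pooled summary can also mislead. If 35 fetuses changed by -15% and 15 by 0% (assumed values), the pooled mean is (35 × -15 + 15 × 0)/50 = -10.5%, which describes neither group.

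**Working it through.** **Inputs.** N = 50 (protocol summary and section 5.2). Historical compromise rate 22/70 and expected split of about 35 and 15 (section 8). The documents give no SD of the change, confidence level or power. The 95% level and every SD below are assumptions.

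**The plan's own figure.** 50 × 22/70 = 15.7 compromised and 50 × 48/70 = 34.3 uncompromised, which agrees with the stated 15 and 35 to within rounding.

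**What the plot's limits show.** They lie 1.96 SD either side of the mean difference. The 95% CI of a mean paired change has half-width t(0.975, n-1)/√n in SDs of the change. At n = 50 this is 2.0096/7.071 = 0.284 SD. The limits are therefore 1.96/0.284 = 6.9 times wider and answer a different question.

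**Precision available at the planned numbers, in SDs of the change.**

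- All fetuses, n = 50: 0.284
- Uncompromised, n = 35: 2.0322/5.916 = 0.344
- Compromised, n = 15: 2.1448/3.873 = 0.554
- Difference, pooled: t(0.975, 48) × √(1/35 + 1/15) = 0.620
- Difference, Welch with equal SDs (df 26.6): 0.634

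**In percentage points, for a range of assumed SDs of percent change (half-widths).**

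| Assumed SD | n = 50 | n = 35 | n = 15 | Difference (Welch) |
|---|---|---|---|---|
| 10 | 2.8 | 3.4 | 5.5 | 6.3 |
| 20 | 5.7 | 6.9 | 11.1 | 12.7 |
| 30 | 8.5 | 10.3 | 16.6 | 19.0 |
| 40 | 11.4 | 13.7 | 22.2 | 25.3 |

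**Why the ROC area does not supply the size of the change.** For two normal groups with equal SD and means d SDs apart, the area is Φ(d/√2). Take two invented cases, uncompromised mean first:

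- Case A: means +40% and +30%, SD 10, so d = 1 and the area is Φ(0.707) = 0.76. Compromised group 30 ± 5.5 = 24.5 to 35.5; difference 10 ± 6.3 = 3.7 to 16.3.
- Case B: means +40% and 0%, SD 40, so d = 1 and the area is again 0.76. Compromised group 0 ± 22.2 = -22.2 to 22.2; difference 40 ± 25.3 = 14.7 to 65.3.

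Discrimination is the same in both. The compromised group clearly responds in A, whereas in B its mean change is centred on zero.

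**Responder proportions (illustrative counts, exact 95% CI).** 35/50: 55.4% to 82.1%. 28/35: 63.1% to 91.6%. 3/15: 4.3% to 48.1%.

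**The case against.** The strongest reply is that this is a pilot that declares description sufficient, and that its central question is diagnostic. ROC is the right method for that question: cases A and B have equal areas because they discriminate equally well. The plot already shows the mean difference and SD-based limits, so anyone with n can derive a pooled paired interval, and nothing is lost that could not be repaired at reporting.

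Much of this stands. The plot suits the aim of describing ranges and should be kept, ROC should be kept, and formal tests are not required. But an interval is itself descriptive and is most needed in a small sample. The primary objective asks for the response to be characterised as well as for its diagnostic value. Pooled limits also cannot be turned into estimates by group.

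A reader might infer two stronger criticisms that the documents do not support:

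- *That the plan makes no comparison by outcome.* Sections 2.4, 4.1 and 4.3 all intend one, and simple descriptive statistics could include summaries by group. What is missing is a stated method that estimates the change by group.
- *That intervals by compromise group would test the predictions of no pulmonary response in section 2.4.* Those predictions concern scenarios 2 (in-utero restriction) and 4 (PPHN), not the compromised group as a whole. That group may also include scenario 3, where a different response is predicted. Section 8 expects one PPHT case, and no margin for absence of effect is given.

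**Conclusion.** The point holds as a mismatch between the named method and the target, and it is worth correcting before analysis. Section 8 uses an agreement plot where a paired change and its precision are needed, and the only method it names for the link with outcome does not estimate the change in each group or the difference between groups.

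At the planned numbers the estimates are feasible but imprecise for the compromised group: half-widths of about 0.28 SD overall, 0.34 SD and 0.55 SD by group, and 0.63 SD for the difference. These figures rest on a 95% level, t-based intervals, equal SDs for the difference, and the 35/15 split. The split applies a rate observed in TGA/IVS to a cohort that section 5.2 also opens to VSD, so the real split may differ. The percentage-point figures depend on assumed SDs. The collected data and the planned plots remain usable.

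**What to change.** Replace the Bland-Altman sentence in section 8 with:

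> Change from baseline to MH will be reported as the mean within-fetus change with a paired 95% CI, overall and by neonatal-compromise group, with the between-group difference and its Welch 95% CI (percent change for VTIs and PIs as in section 6.1.2; absolute change for saturations, oxygen content and any flow that may be near zero at baseline, such as foramen ovale flow). The proportion with a branch-PA PI fall of at least 10% will be given with an exact 95% CI, overall and by group. All comparisons are exploratory. Bland-Altman plots are kept to show individual variation.

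Absolute change is needed for foramen ovale flow because sections 2.3 and 2.4 describe fetuses in whom it is reduced or absent, and percent change is unstable near zero. The scale for the remaining variables (for example FO diameter, septal excursion, ventricular volumes, cDO₂ and cVO₂) should also be fixed before analysis. Any lead variable is for the investigators to choose before analysis. The documents do not single one out: branch-PA PI does not measure the oxygen-content contrast that defines scenario 3, and several cerebral measures are collected.

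The cost is SAP wording and a little more analysis of data already collected, with no added visits or measurements. The downsides are wide intervals in the compromised group and many comparisons, which must be read as exploratory.
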